5.4. Data to be collected and timing of data collection

At each of the study visits, a medical history with symptom assessment, medication review, vital signs, and physical exam will be obtained. As described above, additional data from the PET/CT scan and echocardiogram will be obtained at baseline and at the end of treatment period. One week after completion of the trial, telephone follow-up will be conducted to assess for any adverse events.

Laboratory analysis: Routine labs required for initiation and monitoring of biologic therapy will be collected at the baseline and follow-up cardiovascular visit. At the Baseline and End of Treatment visit, hs-CrP, Hs-troponin, BMP, CBC, lipid panel, and a pregnancy test (women of child-bearing potential before

each PET scan) will be obtained. Inclusion criteria will include TB screening per protocol. Blood samples will also be collected and stored for future analysis of biomarkers of inflammation and myocyte injury.

6. BIOSTATISTICAL ANALYSIS

6.1. Identification of clinical sites participating in the proposed ancillary study. BWH will be the primary site with extrenal advertising and recruitment from hospitals in the surrounding New England area. Based on the power calculations below and assuming a 15% effect size, the study will need to recruit approximately 35 patients which includes a 20% attrition rate. We will perform an interim analysis at 20 patients where a conditional power analysis will be performed for futility of the paired t-test to be performed at the end of the study. This analysis will be computed using PASS Sample Size Software (Version 15) with the observed data from these 20 patients⁸⁰. If the conditional power is less than 15%, the study will curtailed. We believe that the proposed study is reasonable and attainable. [name] is an experienced clinical investigator with a successful track record in psoriasis clinical trials⁸¹⁻⁸⁵. [name] is a recognized expert in quantitative PET and nuclear cardiology imaging, has published widely on these topics, and has extensive experience in conducting clinical trials using imaging endpoints⁸⁶⁻⁸⁹. With external advertising throughout the New England area and social-media, we estimate recruitment rates of 2-4 patients/month and estimate a trial length of ~2.5 years.

6.2. Power Analysis:

Table 2 shows the sample size needed to reach 90% power for an effect size of 15-25% relative improvement in CFR from baseline using a standard deviation of 0.7 at baseline and follow-up and a correlation of 0.7 between baseline and follow-up measurements. Effect sizes were calculated from a baseline mean CFR of 2.4, which is a conservative value derived from a prior study which examined CFR by doppler echocardiography in patients with psoriasis without coronary artery disease⁹⁰. Although data from our retrospective registry demonstrate lower CFR values in patients with psoriasis, this was a selected high-risk population who were clinically referred for PET without objective data on the degree of severity of psoriasis. Thus, we chose to use the conservative estimate of 2.4 for the power calculations.

Table 2. Power calculation

Effect Size	Mean CFR difference (24 weeks – Baseline)	SD	Total Sample Size (85% power)	Total Sample Size (90% power)	Total Sample Size (99% power)
15%	0.36	0.7	23	26	44
20%	0.48	0.7	14	16	26
25%	0.6	0.7	10	11	18

Using a total sample size of 35 evaluable patients and a two-tailed alpha of 0.05, there will be 90% power to detect an effect size of 15% relative improvement in CFR from baseline, estimating a ~20% attrition rate between time of baseline and final PET.

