3.4 Sample size and source of subjects

A total of **35 analyzable patients** will be recruited for participation and the study will be performed at a single-center institution, Brigham and Women's Hospital (BWH). BWH Faulkner Hospital, Newton Wellesley Hospital, and Massachusetts General Hospital, MGH (PI: [name]) will participate as feeder sites. All dermatology clinical assessments will be conducted through the Center for Clinical Investigation (CCI) at the BWH or at the [name] dermatology clinics. All patients will be referred for cardiac PET imaging to BWH, with BWH serving as the Core Imaging Lab and Data Coordinating Center.

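### A baseline CFR of 2.4 is the favourable choice for power, not the conservative one, and 35 is the recruited number in one place and the evaluable number in others

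*Combined protocol and SAP*

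**What the plan says.** Section 6.2 powers the primary paired t-test for a "15-25% relative improvement in CFR from baseline using a standard deviation of 0.7 at baseline and follow-up", with a correlation of 0.7 between the two scans. On the baseline it says: "Effect sizes were calculated from a baseline mean CFR of 2.4, which is a conservative value derived from a prior study". That study used Doppler echocardiography in patients with psoriasis and no coronary artery disease. The group's own PET registry is set aside as a selected high-risk group, "clinically referred for PET without objective data on the degree of severity of psoriasis". The paragraph closes: "Thus, we chose to use the conservative estimate of 2.4 for the power calculations".

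On the sample size, three places speak of 35:

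- Section 3.4 gives the number to be recruited as "35 analyzable patients".
- Section 6.1: "the study will need to recruit approximately 35 patients which includes a 20% attrition rate".
- The closing sentence of Section 6.2: "Using a total sample size of 35 evaluable patients and a two-tailed alpha of 0.05, there will be 90% power" for a 15% effect, and then, in the same sentence, "estimating a ~20% attrition rate between time of baseline and final PET".

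**The concern.** A conservative input to a power calculation is one that, if wrong, is wrong in the safe direction. A reader will therefore take it that a true baseline below 2.4 would leave power intact. Under the plan's own inputs the opposite holds.

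The second matter decides when enrolment ends. Thirty-five recruited with 20% loss leaves 28 pairs; 35 evaluable with the same loss needs about 44 recruited. Staff working from different sections could stop about nine patients apart, and the stated 90% belongs to only one of the two readings.

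**Working it through.** **Inputs.** Relative effect 15%, baseline 2.4, SD 0.7 at each time, correlation 0.7, two-sided 5% level, attrition 20% (Sections 6.1 and 6.2); paired t-test (Section 6.4); registry psoriasis CFR 1.92, SD 0.65, and matched controls 2.3, SD 0.8 (Section 1).

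**Method.** SD of the change = SD × √(2(1 − r)) = 0.7 × √0.6 = 0.542. Power comes from the noncentral t distribution with n − 1 degrees of freedom and noncentrality (change / 0.542) × √n.

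**Step 1: the plan's own table.** For changes of 0.36, 0.48 and 0.60, the pairs needed for 85/90/99% power are 23/26/44, 14/16/26 and 10/11/18. All nine cells of Table 2 reproduce.

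**Step 2: effect of the baseline.** The change is 0.15 × baseline: 0.15 × 2.4 = 0.36, but 0.15 × 1.92 = 0.288. With 28 pairs the noncentrality falls from 0.36/0.542 × √28 = 3.51 to 0.288/0.542 × √28 = 2.81. Power for a 15% effect:

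| Baseline CFR | SD | 26 pairs | 28 pairs | 35 pairs |
|---|---|---|---|---|
| 2.4 | 0.7 | 90.2% | 92.3% | 96.8% |
| 2.3 | 0.7 | 87.6% | 90.1% | 95.5% |
| 2.1 | 0.7 | 81.2% | 84.2% | 91.6% |
| 1.92 | 0.7 | 74.0% | 77.3% | 86.3% |
| 1.92 (registry mean and SD) | 0.65 | 80.0% | 83.1% | 90.8% |

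At SD 0.7, the change detectable with 90% power is 0.345 with 28 pairs and 0.306 with 35. Divided by 0.15, these correspond to baselines of 2.30 and 2.04; below them power is under 90%.

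**Step 3: could 2.4 be conservative under another assumption?**

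- If the SD scales with the mean, the SD at 1.92 is 0.7 × 1.92/2.4 = 0.56. Power is then 92.3% with 28 pairs, the same as at 2.4: neutral.
- If the absolute change is fixed at 0.36 and the SD at 0.7, the baseline plays no part: neutral.
- Only an SD that falls faster than the mean (below 0.56 at 1.92) would make 2.4 conservative.

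**Step 4: the meaning of 35.**

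- Recruited: 26/0.8 = 32.5, so 33 patients, which an approximate 35 covers. 35 × 0.8 = 28 completers give 92.3%.
- Evaluable: 35 pairs give 96.8%, not 90%, and need 35/0.8 = 43.75, so about 44 recruited.

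**Step 5: the interim look.** These are fixed-sample figures. Section 6.1 adds a futility look at 20 patients with a 15% conditional-power threshold. In a simulation at 2.4 and SD 0.7, with conditional power computed under the observed trend (an assumption), power with 28 pairs is about 91%.

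**The case against.** The strongest reply is that little turns on this. Table 2 is right, the trial is a single-arm pilot, and at the planned inputs power is at least 90% on either reading. All of that stands.

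On the label, the authors may have meant only that 2.4 does not presume severely impaired patients. That could explain the first use of the word, but the second ties it expressly to the power calculation. Their reason for not expecting 1.92 is fair, so 1.92 is a sensitivity case, not a forecast.

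On the 35, Section 3.4 speaks of recruiting the analyzable patients, and Section 6.2 mentions attrition in the same sentence as the evaluable ones. This looks more like loose adjectives around one number than two rival designs. That favours the recruited reading, but the text still needs to say so.

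Two stronger readings are tempting and should be resisted:

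- A reader might infer that neither meaning of 35 delivers the stated 90%. The recruited reading does: 26 pairs give 90.2%, and the surplus with 28 comes from rounding up. Only 35 evaluable departs from 90%, and there the plan understates its power.
- A reader might compare the SD-to-mean ratio in the registry (0.65/1.92 = 34%) with the plan's (0.7/2.4 = 29%) and conclude that SD does not track the mean. The like-for-like PET comparison does not support that: from controls to psoriasis the mean ratio is 1.92/2.3 = 0.835 and the SD ratio 0.65/0.8 = 0.8125, so the SD falls about in step with the mean. Two groups settle nothing, but they bar the inference. They also mean that the 83% for the registry pair should not be put down to the lower baseline alone: keeping that pair's SD-to-mean ratio at a baseline of 2.4 (SD 0.8125) gives 83.1% as well.

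**Conclusion.** Two statements are wrong as written; the calculation they surround is right.

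First, with a relative effect and with SD and correlation held fixed, as Section 6.2 does, 2.4 is the favourable choice against the lower registry value. The cost of a lower baseline with 28 pairs runs from about 2 percentage points at 2.3 to 15 at 1.92 (92.3% to 77.3%). That size rests on SD staying at 0.7; with SD proportional to the mean it would be nil, and the label would still be unjustified.

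Second, 35 cannot be both recruited with 20% attrition included and evaluable. The recruited reading agrees with the 90% target; the evaluable reading implies about 97% and about 44 recruited.

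A reader might infer that the trial is underpowered. The documents do not show that: at the stated inputs the 90% target is met on both readings, and nothing establishes that the enrolled baseline will be near 1.92. This is a correction that should be made, not a design flaw.

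**What to change.** 1. Delete the word conservative from both sentences of Section 6.2. The source of 2.4 and the reason for setting the registry aside can stay.
2. Use one definition of 35 in Sections 3.4, 6.1 and 6.2. Wording that fits both attrition statements: *35 enrolled, about 28 evaluable after 20% attrition, giving 92% fixed-sample power (about 91% allowing for the futility look at 20 patients, if conditional power is computed under the observed trend) for a mean CFR increase of 0.36, that is 15% of 2.4.* If 35 evaluable is really intended, state about 97% fixed-sample power and a recruitment target of about 44.
3. Add one sensitivity line for 28 pairs: *fixed-sample power for a 15% effect is 92, 90, 84 and 77% at baselines of 2.4, 2.3, 2.1 and 1.92 with SD 0.7, and 83% at the registry's 1.92 with SD 0.65.*

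The cost is a few sentences. Endpoint and test are unchanged, and so is enrolment on the recruited reading. The one downside is that the stated power will look less favourable at lower baselines.

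### Sections 3.4 and 6.2 make 35 the number analysed and 6.1 makes it the number recruited; on the plan's own inputs 35 evaluable patients give about 97% power, not 90%

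*Combined protocol and SAP*

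**What the plan says.** The sample size is stated in three places.

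- Section 3.4: "A total of 35 analyzable patients will be recruited for participation".
- Section 6.1: for a 15% effect, "the study will need to recruit approximately 35 patients which includes a 20% attrition rate".
- Section 6.2, closing sentence: "Using a total sample size of 35 evaluable patients and a two-tailed alpha of 0.05, there will be 90% power" for a 15% relative improvement. The same sentence ends "estimating a ~20% attrition rate between time of baseline and final PET".

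Table 2 in Section 6.2 gives 26 patients for 90% power and 44 for 99% power at the 15% effect (a change of 0.36 on a baseline mean of 2.4). Its inputs are an SD of 0.7 at both time points and "a correlation of 0.7 between baseline and follow-up measurements". Section 6.4 names the paired t-test as the primary analysis.

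Section 6.1 also plans a futility look at 20 patients: "If the conditional power is less than 15%, the study will curtailed".

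**The concern.** A paired t-test on the change in CFR uses only patients with both PET scans. A patient lost before the final scan is enrolled but not evaluable. If 35 is the number enrolled, fewer than 35 will be analysed. If 35 is the number analysed, more than 35 must be enrolled. The plan says both, and in Section 6.2 it attaches future attrition to a number it has already called evaluable.

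Two things depend on the answer. The first is when recruitment stops: a team following Section 6.1 stops at about 35, and a team following Section 3.4 continues until 35 are analysable. The second is the power reported with the trial. Table 2 puts 26 patients at 90% and 44 at 99%, so 35 evaluable patients must lie between those two levels and cannot correspond to 90%.

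The final number of pairs also enters the interim conditional-power calculation, so leaving it open leaves a free choice there.

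**Working it through.** **Inputs.** From Section 6.2: SD 0.7 at baseline and at follow-up, correlation 0.7, mean change 0.15 × 2.4 = 0.36, two-sided level 0.05, attrition 20%. From Section 6.4: paired t-test.

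**SD of the change.** 0.7 × √(2 × (1 − 0.7)) = 0.542. Standardised change: 0.36 / 0.542 = 0.664.

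**Reproducing Table 2.** Power comes from the noncentral t distribution with n − 1 degrees of freedom and noncentrality 0.664 × √n. The smallest n reaching 85%, 90% and 99% power is:

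| Change | Computed n | Table 2 |
|---|---|---|
| 0.36 | 23 / 26 / 44 | 23 / 26 / 44 |
| 0.48 | 14 / 16 / 26 | 14 / 16 / 26 |
| 0.60 | 10 / 11 / 18 | 10 / 11 / 18 |

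All nine cells agree, so this is the plan's own method.

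**Power and enrolment for a change of 0.36.**

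| Evaluable pairs | Noncentrality | Power | Recruited at 20% attrition |
|---|---|---|---|
| 26 | 3.39 | 90.2% | 26 / 0.8 = 32.5, so 33 |
| 28 | 3.51 | 92.3% | 28 / 0.8 = 35 |
| 35 | 3.93 | 96.8% | 35 / 0.8 = 43.75, so 44 |

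With 35 recruited, nine losses (9 / 35 = 25.7%) still leave 26 pairs.

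**Can another method rescue 90% at 35 evaluable?** No. The normal approximation gives 97.5% and a one-sided test 98.6%. Taking 0.7 as the SD of the change itself gives 84.0% at n = 35, needs 42 for 90%, and no longer reproduces Table 2.

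**Timeline.** Section 6.1 says "we estimate recruitment rates of 2-4 patients/month and estimate a trial length of ~2.5 years". At 2 per month plus about 5.5 months for the 24 weeks of follow-up, 35 enrolled takes 17.5 + 5.5 = 23 months and 44 takes 22 + 5.5 = 27.5 months. Both fit within about 30 months.

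**Interim rule (secondary and illustrative).** The plan does not give these assumptions: known SD, 20 completed pairs, a two-tailed calculation, and remaining patients following the observed trend. With information fraction t = 20/N, conditional power is Φ((z/√t − 1.96)/√(1 − t)) + Φ((−z/√t − 1.96)/√(1 − t)). Setting this to 0.15 gives the stopping limit. The interim z has mean 0 with no effect, and 0.664 × √20 = 2.97 with a change of 0.36.

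| | N = 28 | N = 35 |
|---|---|---|
| Stop if \|z\| is below | 1.19 | 0.97 |
| Chance of stopping, no effect | 77% | 67% |
| Chance of stopping, change 0.36 | 3.7% | 2.3% |
| Overall power with the rule (simulation, 400,000 trials) | 91% | 96% |

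The choice of N changes the interim decision in about 10% of trials with no effect and 1.5% with a change of 0.36.

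**The case against.** The best defence is that the intended meaning can be recovered. Section 6.1 is explicit that 35 is to be recruited and includes attrition, Section 3.4 also uses the verb recruit, and the Section 6.2 sentence ends with attrition still to come. Read that way, 35 × 0.8 = 28 pairs give 92.3%, consistent with a planned 90%, and 26 / 0.8 = 33 is close to 35. No enrolment figure of 44 appears anywhere. *Evaluable* is also undefined, and might mean patients who remain in the study after the baseline scan, since Sections 9.1 and 9.3 allow exclusion or discontinuation on imaging findings. Nothing in Table 2 is wrong, and no reading leaves the trial short of 90% on its own assumptions.

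Most of this stands. 35 recruited is probably what was meant, and the practical effect is limited. But two of the three statements say otherwise, one of them in the section headed as the sample size. The alternative meaning of *evaluable* is inference; the plan does not state it. Reading 90% as a minimum does not remove the conflict between sections.

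On the interim rule, Section 6.1 does say the calculation uses the data observed in the 20 patients. That leans towards the observed trend, but does not settle what is assumed for the patients still to come, and does not give the final number of pairs.

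**Conclusion.** The point holds. The description of 35 conflicts between Sections 3.4 and 6.2 on one side and Section 6.1 on the other. The power stated for 35 evaluable patients is about 7 percentage points too low on the plan's own inputs (96.8% against 90%). The two readings differ by about nine enrolled patients.

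This should be fixed, but it does not threaten the trial: power is 92.3% or 96.8% depending on the reading, and in the illustrative calculation the futility rule leaves it at about 91% or 96%. These figures rest on the plan's SD of 0.7, correlation of 0.7 and change of 0.36. The margin depends on the correlation: at 0.6, for example, 28 pairs would give 83.5% and 35 pairs 91.1%. That is a further reason to be clear about which number is the target. The interim figures also rest on assumptions the plan does not state, and the conclusion does not depend on them.

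**What to change.** Use one statement in Sections 3.4, 6.1 and 6.2. If 35 recruited is meant: *enrol about 35; with 20% attrition about 28 evaluable pairs; about 92% power for a mean change of 0.36 (90% needs 26 pairs)*. Remove *analyzable* and *evaluable* as descriptions of 35. If 35 evaluable is truly intended, restate the power as about 97% and the enrolment as about 44.

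In Section 6.1, use the same final number of pairs in the conditional-power rule. Before the look, state whether the remaining patients are assumed to follow the observed trend or the planned 0.36, and whether the 20 patients are 20 completed pairs.

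The cost is wording in three sections. No patients are added if 35 recruited is meant. About nine more are enrolled if 35 evaluable is meant, which the plan's recruitment rate and trial length allow.

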6.3. Study endpoints

Primary Endpoint: Change (from baseline) in CFR, as measured by PET imaging at 24 weeks after initiation of Tildrakizumab

Secondary Endpoints:

- (1) Correlation between the change (from baseline) in global CFR and psoriasis skin severity score (PGA, BSA PASI) at 24 weeks after initiation of Tildrakizumab;
- (2) Change (from baseline) in peak-stress global myocardial blood flow (in mL/min/g) at 24 weeks after initiation of Tildrakizumab;
- (3) Change (from baseline) in peak-stress global coronary vascular resistance (in mm Hg/mL/min/g) at 24 weeks after initiation of Tildrakizumab;
- (4) Change (from baseline) in LV peak GLS and E' at 24 weeks after initiation of Tildrakizumab
- (5) Correlation of the change (from baseline) in LV peak GLS and E' with the global CFR at 24 weeks after initiation of Tildrakizumab
- (6) Change in serum biomarkers of inflammation (hs-CRP), myocyte injury and strain (hs-Troponin, NT-proBNP) at baseline and 24 weeks after initiation of Tildrakizumab.
- (7) If the primary endpoint is positive, secondary exploratory analyses will use stored aliquots of plasma and serum to IL-6, TNFRII, ICAM, Glyc-A, p-selectin, e-selectin, sCD40L, adiponectin, and MCP-1.

6.4. Statistical methods

To test *the central hypothesis*, that reducing endothelial cell activation and dysfunction by treatment with Tildrakizumab will quantitatively improve CFR as measured by PET over 24 weeks, we will perform a paired t-test to assess the Δ CFR between baseline and follow-up for each subject.

If a significant change in CFR after the initiation of Tildrakizumab is observed, we will perform secondary analyses of association between other markers of inflammation also implicated in atherosclerosis with Δ CFR. Significance of associations with other inflammatory markers and Δ CFR will be adjusted using the Bonferroni correction.

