- 3.3.3. Change (from baseline) in peak-stress global coronary vascular resistance (in mm Hg/mL/min/g) at 24 weeks after initiation of Tildrakizumab
- 3.3.4. Change (from baseline) in LV peak global longitudinal strain (GLS) and E' at 24 weeks after initiation of Tildrakizumab
- 3.3.5. Correlation of the change (from baseline) in LV peak GLS and E' with the global CFR at 24 weeks after initiation of Tildrakizumab

- 3.3.6. Change in serum biomarkers of inflammation (hs-CRP), myocyte injury and strain (hs Troponin, NT-proBNP) at baseline and 24 weeks after initiation of Tildrakizumab.
- 3.3.7 If the primary endpoint is positive, secondary exploratory analyses will use stored aliquots of plasma and serum to IL-6, TNFRII, ICAM, Glyc-A, p-selectin, e-selectin, sCD40L, adiponectin, and MCP-1.

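### Section 6.4 adjusts the exploratory marker associations by Bonferroni with no stated divisor; Holm's procedure gives the same error control, never rejects fewer hypotheses, and costs only wording

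*Combined protocol and SAP*

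**What the plan says.** Section 6.4 (Statistical methods) names one test, a paired t-test on the change in CFR, and one multiplicity rule. If CFR changes significantly, associations between other inflammatory markers and the change in CFR are examined, and their significance "will be adjusted using the Bonferroni correction". Section 6.4 neither lists the markers nor gives the divisor.

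Item (7) of section 6.3, repeated as 3.3.7 under Specific Aims, sets the same condition on the primary result, calls the analyses exploratory, and names "IL-6, TNFRII, ICAM, Glyc-A, p-selectin, e-selectin, sCD40L, adiponectin, and MCP-1". That is nine markers.

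Items (1) to (6) of section 6.3 are not conditional on the primary result. Item (4), for example, is "Change (from baseline) in LV peak GLS and E' at 24 weeks after initiation of Tildrakizumab". The plan gives no test, significance level or multiplicity statement for any of them, and does not say whether they are descriptive. The "two-tailed alpha of 0.05" in section 6.2 belongs to the power statement for the primary endpoint.

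**The concern.** Bonferroni holds every marker to the strictest threshold, even after other markers in the family have been declared significant. Holm holds only the smallest p-value to that threshold and relaxes it step by step, with the same guarantee. In a study of about 28 completers, a marker association that Holm would detect can be missed for no return in error control. Because no divisor is stated, the threshold itself is also open: nine markers give 0.0056, but adding hs-CRP, also an inflammatory marker, would give 0.05/10 = 0.005.

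A smaller matter sits beside this. Items (1) to (6) have no rule for how their p-values are to be read, while Aim 2 words some of them (GLS, E' and their correlations with the change in CFR) as hypotheses to be tested.

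**Working it through.** **The plan's own figure.** Inputs from section 6.2: "using a standard deviation of 0.7 at baseline and follow-up and a correlation of 0.7 between baseline and follow-up measurements", and "Effect sizes were calculated from a baseline mean CFR of 2.4".
- SD of the difference = 0.7 × √(2 × (1 − 0.7)) = 0.542. A 15% effect is 0.15 × 2.4 = 0.36.
- A paired t-test at two-sided 0.05 needs 26 patients for 90% power, as in Table 2; the other eight cells also reproduce.
- 26/(1 − 0.2) = 32.5, so 33, close to the "approximately 35 patients which includes a 20% attrition rate" of section 6.1. That reading leaves 35 × 0.8 = 28 completers. Section 6.2 instead says "Using a total sample size of 35 evaluable patients", so 35 is also shown below.

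**Bonferroni on nine markers.** Threshold 0.05/9 = 0.0056.
- Family-wise error, all nulls true and independent: 1 − (1 − 0.05/9)^9 = 4.9%.
- With no adjustment: 1 − 0.95^9 = 37.0% (26.9% at a common correlation of 0.5).

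**Holm on the same nine.** Order the p-values and compare them in turn with 0.05/9, 0.05/8, … 0.05/1, stopping at the first failure.
- *Error control.* If m0 nulls are true, a first false rejection requires some true-null p-value at or below 0.05/m0. The probability is at most m0 × 0.05/m0 = 0.05, whatever the dependence.
- *Never fewer rejections.* Every threshold is at least 0.05/9, so any p-value that passes Bonferroni also passes Holm.
- *Same first step.* Both need the smallest p-value at or below 0.05/9, so they always agree on whether any marker is significant.

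**Size of the gain.** The correlations are assumptions; the documents give none. Bonferroni power by Fisher's z at n = 28:
- r = 0.5: atanh(0.5) × √25 = 2.75 against a critical value of 2.77, power 49%.
- r = 0.3: atanh(0.3) × √25 = 1.55 against 2.77, power 11%.

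Holm's power was simulated with Pearson tests (40,000 trials per scenario):

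| Markers truly associated (n = 28) | Correlation between markers | Bonferroni | Holm |
|---|---|---|---|
| All nine, r = 0.5 | 0.4 | 49% | 61% |
| Three, r = 0.5 | 0.3 | 49% | 51% |
| One, r = 0.5 | 0.3 | 49% | 49% |
| All nine, r = 0.3 | 0.3 | 11% | 12% |

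The first row is 9 × 0.49 = 4.4 against 9 × 0.61 = 5.5 markers found. The last row becomes 11% against 13% at a between-marker correlation of 0.4. At n = 35 the first row is 64% against 77%. In the three-marker row, Holm's chance of a false positive among the six null markers was about 4%, below 5%.

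**Secondary note: items (1) to (6).** Count, one test per named measure: 3 skin-score correlations + 1 stress flow + 1 resistance + 2 (GLS, E') + 2 correlations with CFR + 3 serum biomarkers = 12. Assume 0.05 for each and all nulls true.
- Independent: 1 − 0.95^12 = 46%.
- Common correlation 0.3, 0.5, 0.7, 0.9: 40%, 32%, 23%, 13%.
- Correlation of 0.5 to 0.9 only within each group of related endpoints: 42% to 32%.
- The four Aim 2 tests alone, independent: 1 − 0.95^4 = 18.5%.

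The count is not fixed. Section 5.3 measures E' at two mitral annular sites; analysed separately, these would give 14 tests and 1 − 0.95^14 = 51% if independent.

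**The case against.** Bonferroni is a legitimate, conservative choice for an exploratory biomarker screen, and the plan sets no power target for it. Holm's gain is large only if nearly all nine markers are strongly associated with the change in CFR; in the other scenarios it is about two points or less. All of that stands. It limits the size of the point but gives no reason to prefer Bonferroni.

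Uncorrected secondary endpoints are also common in a single-arm pilot with one primary endpoint and one named primary test, and the plan has no rule that turns a secondary p-value into a success. That stands too, and is why the secondary note asks only for clarification.

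Three stronger readings are tempting, and the documents do not support them:
- A reader might infer that multiplicity control is the wrong way round and that Bonferroni buys nothing. It does buy something: making the markers conditional on the primary result does not control error among the nine, whereas Bonferroni holds it to 4.9% against 37.0% unadjusted if independent.
- A reader might put a floor of about 28% under the false-positive chance for items (1) to (6). That needs a common correlation of about 0.6, which the documents do not give; at 0.9 the figure is 13%.
- A reader might take Hypothesis #2 to require both GLS and E' to be significant. Its wording joins a systolic and a diastolic prediction and does not make them jointly necessary.

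**Conclusion.** The point holds as a free improvement of low severity. Holm can replace Bonferroni with no loss of family-wise error control, and the family should be named. At n = 28 the gain in per-marker power runs from effectively nothing (one associated marker) to 12 points (all nine at r = 0.5), under assumed correlations. It never changes whether any marker is significant. The divisor of nine is inferred from 6.3(7), since 6.4 does not state it.

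The absence of a statement for items (1) to (6) is a gap in labelling. The range of about 13% to 46% applies only if all 12 nulls are true, each is tested at 0.05, and p-values are read as findings; the plan states none of these. The paired t-test on CFR and its conclusion are untouched.

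**What to change.** In section 6.4, replace 'Bonferroni correction' with 'Holm step-down procedure over the nine markers named in 6.3(7)'. This also settles the divisor. It changes no sample size, visit or measurement. The one trade-off is that Holm has no simple matching simultaneous confidence intervals, so marker associations would be reported with nominal 95% intervals beside the Holm-adjusted p-values.

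As a clarification in 6.3 or 6.4, state that secondary endpoints (1) to (6) are descriptive and reported as estimates with 95% confidence intervals. The cost is that Aim 2 results would be worded as estimates rather than as tested claims. Both changes should be made before the data are examined.
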